11.1.3 Secondary Endpoint: Analysis of Seizure Outcomes

Surgical outcome classification will be reported by tabulating the Engel and ILAE class frequency distribution at each scheduled follow-up, among subjects completing that follow-up visit. The change in surgical classification between visits may be described by performing a cross-tabulation of the classifications at subsequent visits. The classifications are described in more detail in Appendix B.

For the Engle classification, there are several classification terms that can be subjective in nature, so further definitions are provided to the sites, as follows:

- the term “disabling seizures” includes all focal seizures *except*
 - those without impairment of consciousness or responsiveness (simple partial seizures) involving subjective sensory or psychic phenomena only
- The term “worthwhile improvement” is defined as $\geq 50\%$ seizure reduction compared to baseline.

Seizure frequency will be characterized by calculating the rate of seizure occurrence within specific follow-up time periods (count of reported events/reported time frame). Follow-up time periods of interest include all follow-up and between-visit follow-up periods (e.g., procedure to Month 3) to characterize the longitudinal course of seizure frequency. For each time period, descriptive statistics of subject-specific rates characterize the distribution of observed seizure rates. The change from baseline in seizure rates may also be calculated by calculating the difference in rate between a follow-up period and the baseline rate of seizures occurring prior to treatment (count of reported events/reported time frame). Since subjects may have different baseline seizure rates, the relative change from baseline in the event rate (r)

$$\frac{(r_{\text{follow-up}} - r_{\text{baseline}})}{r_{\text{baseline}}}$$

will also be calculated to scale the degree of improvement relative to the baseline rate. These analyses may be repeated for subsets of seizures with specific classifications to characterize the frequency of different seizure types.

The primary analysis of seizure frequency will include subjects with at least 70 completed diary days in each 3 month period from procedure through 12 months and at least 140 diary days in each 6 month period from 12 months through study completion. To account for incomplete diary completion, sensitivity analyses may be performed by including subjects with less than the required level of diary completion and by using the number of days with completed diary entries to determine the denominator in the event rate calculation.

Seizure frequency may be further characterized by calculating the *proportion of responders*. A responder is a subject whose seizure frequency in a specified 3-month interval is reduced by $\geq 50\%$ as compared to the 3-month Baseline Phase.

Seizure free days may be further characterized by calculating the percent change in seizure-free days that subjects experience during a specified 3-month interval compared to Baseline. In order to make the 3 month follow-up intervals and the Baseline Phase comparable, the number of days actually recorded will be prorated to an 84-day interval for both intervals. Seizure-free days may also be expressed as a proportion of the number of follow-up days with available diary data.

Freedom from seizures with altered awareness will be reported using Kaplan-Meier curve analysis. Seizures with altered awareness include those categorized as either “impairment of consciousness or responsiveness” or “evolving to a bilateral, convulsive seizure”. The time to event analysis will exclude seizures that occur within the first 4 weeks post-procedure. The event time will be calculated using the earliest post-treatment date of a seizure with altered awareness, as reported in subject diaries. The censoring date will be the last completed diary date for subjects without seizures with altered awareness. The Kaplan-Meier analysis may be repeated for freedom from all seizures, seizures with other classifications, and inclusion of seizures within the first 4 weeks post-procedure. The log-log transformation will be used to calculate 95% confidence intervals. The time point of primary interest is 24 months.

Longest seizure-free interval will be characterized with descriptive statistics for each 3-month period and cumulatively over consecutive 3-month periods. The seizure-free interval will be

measured as the number of completed diary days without a seizure since the most recent post-treatment seizure or the beginning of the time period being characterized (e.g. since the day of treatment for the cumulative analysis), whichever is more recent. The longest seizure-free interval will also be calculated for the baseline period, which permits calculation of the change in the longest seizure-free interval from baseline for each subject. The change in longest seizure-free interval may be characterized with descriptive statistics.

Rescue medication use will be analyzed with both a Kaplan-Meier analysis to describe the freedom from use of any rescue medication and a descriptive statistics analysis of the frequency of rescue medication use (number of occasions that rescue medication is required / follow-up time). These analyses will be performed using the same methods as the freedom from seizures and seizure frequency analyses above, but with rescue medication use as the event for analysis rather than seizures.

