Surgical outcome classification will be reported by tabulating the Engel and ILAE class frequency distribution at each scheduled follow-up among subjects completing that follow-up visit. The change in surgical classification between visits may be described by performing a cross-tabulation of the classifications at subsequent visits.

Freedom from seizures with altered awareness will be reported using Kaplan-Meier curve analysis of the time to first seizure, as reported in patient diaries. The time to event analysis will exclude seizures that occur within the first 4 weeks post-procedure. The Kaplan-Meier analysis may be repeated for freedom from all seizures, seizures with other classifications, and inclusion of seizures within the first 4 weeks post-procedure. The log-log transformation will be used to calculate 95% confidence intervals. The time point of primary interest is 24 months.

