- A calendar to record daily seizure activity and missed AED doses
- Other relevant information (e.g., new type of seizure)

Subjects may prefer to use their own diary format (paper or electronic); these will be allowed as long as the subject's diary collects the information listed above.

Subjects may also use the diary to record the following (although this information may be elicited by direct questioning of the subject during a study visit):

- Changes to epilepsy and non-epilepsy medications
- Use of rescue medications
- Recording of non-study-related visits to the doctor, hospital or emergency room.
- Comments section to record other relevant information (e.g., new type of seizure)

Instruction for Diary Completion

At the Baseline visit, and again prior to discharge, the investigator or authorized delegate will instruct the subject/caregiver on proper diary completion. This instruction will include:

- Importance of accurate diary-keeping
- Explanation of the seizure classification key
- How to complete the diary:
 - Recording of seizure activity
 - If no seizures occurred on that day, the subject will be instructed to tick the "no seizure" box for that day
 - If subject missed any dose(s) of their epilepsy medications, the subject will be instructed to tick the "missed epilepsy dose" box for that day
 - Explanation that the NAV (not available) designation on a calendar day is for investigator use only
 - How to record medication changes and use of rescue medications
 - How to record non-study-related visits to the doctor, hospital or emergency room
 - What might be recorded in the "other" section

Recording Seizures

Subjects or their caregiver will keep a seizure diary starting the day after discharge. A new diary is provided at subsequent appointments. The subject or caregiver will record the number and type of seizures each day.

Sites will be instructed to take measures to ensure that diary entries are faithfully recorded in order to minimize missing diary data. Subjects will be trained on the importance of accurate diary-keeping.

At each visit the investigative staff will review the diary with the subject and/or caregiver and address any concerns with diary completion. If seizure information is not available for a specific diary day, the coordinator will tick the “NAV” box for that day. An example of a diary day is shown below.

Sun _____	 NAV
 Missed epilepsy dose	

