12.3 Duration variables

Months for this study are defined as 28-day intervals and are referred to as "study months" to distinguish the interval from calendar months. Duration in study months is calculated as the number of days divided by 28. Duration in study years is calculated as the number of days divided by 12 study months.

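### The Kaplan-Meier rule counts unrecorded diary stretches as seizure-free time and takes events from diaries alone, so 24-month freedom can be overstated by an amount the plan does not bound

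*SAP*

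**What the plan says.** SAP 11.1.3 defines the event as follows: "The event time will be calculated using the earliest post-treatment date of a seizure with altered awareness, as reported in subject diaries". Subjects without an event are handled in the next sentence: "The censoring date will be the last completed diary date for subjects without seizures with altered awareness". Protocol 10.1.3 likewise analyses "time to first seizure, as reported in patient diaries". Early seizures are set aside: "The time to event analysis will exclude seizures that occur within the first 4 weeks post-procedure". For the horizon, the SAP says: "The time point of primary interest is 24 months".

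Missing diary days are identifiable. Under Protocol Appendix B, "If seizure information is not available for a specific diary day", the coordinator marks that day NAV.

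The SAP allows for such days in its other diary analyses:

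- The primary seizure-frequency analysis requires "at least 70 completed diary days in each 3 month period from procedure through 12 months", and 140 days in each later 6-month period (SAP 11.1.3).
- Rates leave days without data out of the denominator (SAP 12.4).
- The longest seizure-free interval counts completed diary days only (SAP 11.1.3).
- Seizure-free days are prorated to a common 84-day interval (SAP 11.1.3).

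The Kaplan-Meier analysis has no counterpart: no maximum gap, no minimum coverage and no second source of events. SAP 11.1.3 applies the same methods to freedom from rescue medication.

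**The concern.** A subject with a long run of NAV days followed by one completed day stays in the risk set, event-free, through the whole run. If a qualifying seizure fell in that run and none is recorded later, the subject is counted as seizure-free. If one is recorded later, the event is only delayed.

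The second gap in the rule is the source of events. Protocol Appendix B sends new seizure types to Seizure Classification and Adverse Event forms, but nothing there feeds the Kaplan-Meier event. Read literally, a subject whose only qualifying seizure is on such a form has no event date under the first sentence and does not clearly fall under the censoring sentence either. The programmer would have to decide.

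At stake is the 24-month point on a seizure-freedom curve from a study whose results, according to SAP section 9, will help to plan a larger pivotal trial. Enrolling more subjects would not remove an error of this kind.

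**Working it through.** **The plan's own figure.** The only computed figure is the roughly 80% chance of seeing a 5% adverse event at least once in 30 subjects: 1 − 0.95^30 = 0.785. It reproduces, but does not bear on the Kaplan-Meier rule.

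**Inputs from the documents.**
- Study month: "Months for this study are defined as 28-day intervals" (SAP 12.3), so 24 months = 24 × 28 = 672 days.
- Four weeks excluded: 672 − 28 = 644 days at risk.
- Diary gaps tolerated for seizure frequency: 1 − 70/84 = 1 − 140/168 = 16.7%. This limit does not apply to the Kaplan-Meier analysis.
- One subject in 30: 1/30 = 3.3 points.

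**Assumptions, because the documents give no figure.** Half the subjects never have a qualifying seizure. The others have a constant rate of r per 336-day study year. A share m of days is unrecorded, at random.

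**Formulae.** With L = r/336 per day:
- true 24-month freedom = 0.5 + 0.5 × exp(−644 L)
- freedom under the SAP rule = 0.5 + 0.5 × exp(−644 L (1 − m))

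Example, r = 1 and m = 1/6: 644/336 = 1.917. True: 0.5 + 0.5 × exp(−1.917) = 0.5 + 0.5 × 0.147 = 57.4%. SAP rule: 0.5 + 0.5 × exp(−1.597) = 0.5 + 0.5 × 0.202 = 60.1%. The excess before rounding is 2.8 points.

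Excess in percentage points:

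| Seizures per study year (r) | 16.7% missing | 30% missing | 50% missing |
|---|---|---|---|
| 0.5 | 3.3 | 6.4 | 11.8 |
| 1 | 2.8 | 5.7 | 11.8 |
| 2 | 1.0 | 2.3 | 6.3 |
| 4 | 0.1 | 0.2 | 1.1 |
| 12 | 0.0 | 0.0 | 0.0 |

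The excess is never negative, because a hidden seizure makes a subject's first recorded event later or absent, never earlier. This concerns what the curve estimates when other censoring is unrelated to seizures. In one small data set, a delayed event that falls on a depleted risk set can move the estimate slightly the other way.

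**Does censoring at the start of the gap repair it?** Simulated cohorts of 6,000, half truly free, the others at 1 seizure per study year:

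| Gap pattern | True | SAP rule | Censored at gap start |
|---|---|---|---|
| 168 days in 30% of subjects, at random | 57.2% | 58.6% | 57.3% |
| 168 days in 30%, at the first seizure if there is one | 57.9% | 64.2% | 64.1% |
| 84 days in 50%, at the first seizure if there is one | 58.3% | 67.0% | 71.6% |

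It works when gaps are unrelated to seizures. When they are related, it does not help in one case and does worse in the other. It cannot be the only remedy.

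**The case against.** The best defence is that long, seizure-hiding gaps should be uncommon. Staff review the diary with the subject or caregiver, NAV is meant for days on which information really is unavailable, and there is a visit or call every month through Month 24. A seizure known from an admission is available information and could be entered. Months of NAV days would mean repeated failed contacts, and nothing in the documents suggests 50% missing. The analysis is descriptive and secondary, and sampling error is far larger: the exact 95% interval for 17/30 is 37% to 75%. All of that stands, and it limits how much the point matters. These safeguards reduce or flag gaps, but they do not say how the analysis treats one. The worst-case imputation in SAP section 17 is optional, and its timing rule addresses subjects who exit early, not gaps within follow-up.

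Three stronger readings are tempting, and the documents do not support them.

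- *A subject in Engel class II who is seizure-free on the curve shows the rule has failed.* SAP 11.1.3 counts as disabling some focal seizures without impaired consciousness, namely those with motor or autonomic components. Such a subject can be classified correctly on both measures. ILAE classes from 3 upwards rest on seizure days, not on awareness.
- *This curve is the seizure result of primary interest.* The SAP gives that status to the 24-month time point. The secondary endpoint is framed by seizure frequency and surgical outcome class.
- *Other forms would routinely hold the missed relapses.* Under Protocol 9.1 pre-existing conditions are adverse events only if they worsen, and the contents of the case report forms are not shown.

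**Conclusion.** The point holds in a limited form. The rule uses diary events only, censors at the last completed diary date and makes no provision for earlier gaps, so it credits unrecorded time as seizure-free. Freedom at 24 months can be overstated, and the plan sets no bound on how much. A reader might infer that it *is* overstated. The documents do not show that, because a gap matters only if it hides a qualifying seizure, and most if none is recorded later.

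Under the stated assumptions the excess is about 0 to 3 points at 16.7% missing and up to about 12 points when seizures are rare and half the days are missing. It is negligible for subjects with frequent seizures. The seizure rates, the share truly free and the missingness are all assumed. The change is worth making because it is cheap and the bias has one direction, but it does not threaten the study's main conclusions.

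**What to change.** Revise SAP 11.1.3 as follows.

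1. Count as an event any seizure after week 4 that is documented as altered-awareness in the diary or on any other case report form, such as Adverse Event or Seizure Classification. Do not infer an event from an Engel or ILAE class alone. List and query subjects whose class appears to conflict with their Kaplan-Meier status.
2. Report diary coverage for subjects counted as seizure-free. Define a long NAV gap before analysis and commit to two sensitivity analyses for such gaps before the censoring date. One treats the gap as an event at its start or as interval-censored. The other censors at the start of the gap, with a note that this removes bias only if gaps are unrelated to seizures.
3. Apply the same gap handling to the rescue-medication Kaplan-Meier analysis.

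The cost is SAP text and a little programming. NAV days are already marked, but whether the other forms record awareness status and dates should be checked first. The estimate may become slightly less favourable.

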11.1.4 Secondary Endpoint: Analysis of Quality of Life

Quality of life is assessed with the QOLIE-31 instrument. QOLIE-31 scores at baseline and each scheduled follow-up visit will be characterized using descriptive statistics. In addition, the per-subject paired change from baseline will be calculated and descriptive statistics reported for each scheduled follow-up visit. These analyses may be repeated for the QOLIE-31 sub-domains.

Longitudinal analysis of the QOLIE-31 scores may be performed using a GEE repeated measures model with a working AR1 correlation structure to estimate the mean (with 95% confidence intervals) of the QOLIE-31 over time while accounting for within subject correlation. Baseline QOLIE-31 and visit (categorical) will be included as covariates in the model. The estimate of QOLIE-31 score at 24 months is of primary interest.

Finally, the proportion of subjects with a change from baseline in QOLIE-31 score of 13 points or more will be calculated at each follow-up visit. The threshold of 13 points is based on previous literature estimating 13 points of QOLIE-31 to be the minimum clinically important difference.¹

Further analyses related to subjects' quality of life will be performed with descriptive statistics of responses to the functional assessment (employment status, education level, driving status, and living arrangements) and subject satisfaction with the results of treatment.

12 General Statistical Considerations

12.1 Descriptive Statistics

Standard summary statistics will be calculated for all study variables to be reported. For continuous variables, statistics will include means, standard deviations, medians and ranges. Categorical variables will be summarized by frequency distributions.

Confidence intervals may be reported, as appropriate, using the methods listed below. A 95% confidence interval for the mean may be reported using the t-distribution method. A 95% confidence interval for the proportion may be reported using the Clopper-Pearson exact method.

¹ Wiebe S, Matijevic S, Eliasziw M, Derry PA. Clinically important change in quality of life in epilepsy. *J Neurol Neurosurg Psychiatr* 2002;73(2):116-20.

12.2 Disposition of Subjects

All subjects that sign the informed consent form (ICF) will be accounted for by reporting

1. Number of subjects that sign the ICF/enroll
2. Number of subjects that enroll and meet all eligibility criteria
3. Number of subjects that are eligible for treatment (complete the Baseline Phase and meet the treatment criteria)
4. Number of subjects that exit the study prior to LITT treatment
5. Number of subjects that undergo LITT treatment
6. Number of subjects that complete each follow-up visit
7. Number of subjects that exit the study after LITT treatment but prior to the Month 24 visit.

12.3 Duration variables

Months for this study are defined as 28-day intervals and are referred to as "study months" to distinguish the interval from calendar months. Duration in study months is calculated as the number of days divided by 28. Duration in study years is calculated as the number of days divided by 12 study months.

12.4 Rate variables

Rates will be calculated as the ratio of the number of events divided by the number of days over which data collection occurred. Rates may be reported as events per day, per study month, or per study year. For diary data, days on which episode data is not available will not be included in the denominator.

12.5 Protocol deviations

The number of protocol deviations, number of subjects in which the deviations occur, and proportion of subjects with at least one deviation will be reported for all deviations and by sub-categories of deviations (e.g. informed consent, visit compliance, etc.).

12.6 P-values

While no hypothesis tests are specified, p-values may be used descriptively to report comparisons among sub-groups of subjects or to describe one-sample changes from baseline. P-values will be reported to a maximum of three decimal places with values < 0.001 being denoted as "<0.001". For p-values greater or equal to 0.01, two decimal places will generally be reported. One-sided p-values < 0.025 and two-sided p-values less than 0.05 will be considered statistically significant.

12.7 Time Point of Interest

The study was designed to follow subjects through 24 months post-procedure and 24 months has been identified as a time point of primary interest. Analyses will be performed to assess the consistency of study endpoints over the 24 month time period and the degree of predictability of later outcomes based on outcomes observed at earlier time points (e.g. correlation between seizure rate for the time period of 6 to 12 months and seizure rate for the time period of 12 to 24 months).

13 Subgroup Analyses

Descriptive subgroup analyses for each endpoint will be performed to characterize the consistency of overall study estimates across the following pre-specified groups:

1. Age (tertiles of age)
2. Race (white vs non-white)
3. Gender (male vs female)
4. Baseline seizure frequency (tertiles of baseline seizure frequency)

5. Time since epilepsy diagnosis (tertiles of years since diagnosis)
6. Prior/concurrent VNS treatment (yes vs no)

Subgroup results will only be reported for subgroups that have at least 5 subjects since the smaller the sample size in a subgroup, the less likely it is that the observed results will be generalizable to the subgroup population.

Additional ad hoc subgroup analyses may be performed after all subjects have been enrolled, depending on the subject demographics and available sample size.

14 Treatment Factors Analyses

Descriptive analyses for each endpoint will be performed to characterize the potential relationship between treatment factors and study endpoints.

Treatment factors that will be analyzed include:

1. Complete versus incomplete LITT procedure
2. Abnormal findings on post-op images (e.g. edema, hemorrhage, infarction, or collateral damage)
3. Trajectory anatomic measurements
4. Ablation volume

15 Data Handling

